#### 4.2.6.3 Sensitivity analyses for the primary outcome variable

Sensitivity analyses for the primary and key secondary endpoints based on different missing data mechanism assumptions including those expected to be more conservative, such as missing not at random (MNAR), may be used to explore the robustness of any treatment effect including multiple imputation approaches, if the amount of missing data warrants further investigation. Details using multiple imputation techniques are specified in [Appendix 8.1](#).

To explore alternative approaches other than the primary analysis treatment policy strategy for exploring the impact of rescue medication use, the following sensitivity analyses may be performed for the change from baseline in ISS7 at Week 12 primary endpoint, and may also be repeated for other secondary endpoints if appropriate:

- Rescue medication use: ISS7 treated as missing for 1 day after the day of any post baseline rescue therapy use (but keep values recorded on the day of rescue use), however any ISS7 recorded as 3 (worst score) will not be set to missing. All data after use of restricted medication will be treated as missing. MMRM analysis as described for the primary model above will be performed on the remaining available data whereby as in the primary analysis, weekly scores will only be derived if there remains at least 4 days with evaluable data.
- Substantial rescue medication use: ISS7 treated as missing after substantial use of rescue medication beyond Week 6, or after any use of restricted medication at any time post baseline. Substantial use will be defined as >2\*licensed dose of pre-randomisation antihistamine every day or every two days, for at least 5 consecutive days. Those set to missing data will be imputed by WOCF method. Multiple imputation (MI) techniques (see [Appendix 8.1](#)) will be used to impute data missing for other reasons at Week 12 only.

ISS7 will be analysed using an Analysis of covariance (ANCOVA) model, containing the same covariates and factors as the primary analysis model.

#### **4.2.7 Secondary outcome variables**

##### **4.2.7.1 Change from baseline UAS7**

The key secondary endpoint of change from baseline in UAS7 at Week 12 for both benralizumab 60 mg and benralizumab 30 mg treatment groups will be analysed using an MMRM model in a similar way to that described for the primary endpoint analyses (Section 4.2.6.1).

The dependent variable will be the change from baseline in UAS7 at post-baseline protocol-specified visits up to Week 24, and baseline UAS7 will be included as a covariate as well as the other covariates listed for the primary endpoint analysis.

Descriptive summary statistics for scores and change from baseline in UAS7 will be produced by treatment group and visit.

Sensitivity analyses for the key secondary endpoint may be considered if appropriate for the amount rescue medication usage or missing data, respectively. Details are described above for the primary endpoint.

The secondary endpoint of change from baseline in UAS7 at Week 24 will be analysed using the same method as the key secondary endpoint.

The change from baseline in UAS7 at Week 52 will be analysed with MMRM model as described above, comparing effects on the Q4W and Q8W maintenance regimens.

##### **4.2.7.2 Proportion of responders of UAS7**

The proportion of responders ( $UAS7 \leq 6$ ) at Weeks 12 and 24 will be compared between the benralizumab 60 mg and placebo treatment groups, and the benralizumab 30 mg and placebo treatment groups, respectively, using logistic regression. The model will include terms for treatment group, region and baseline in UAS7. If the model does not converge due to small proportions, only descriptive statistics will be presented.

The results of the analyses will be presented as an odds ratio, together with its associated 95% CIs and 2-sided p-value. Results will also be transformed into a difference in proportions for ease of interpretation. The number and percentage of responders will also be summarised by randomised treatment.

The proportion of participants with complete UAS7 response ( $UAS7 = 0$ ) at Weeks 12 and 24 will be analysed using logistic regression in a similar way as described above.

The responder analyses described above use a treatment policy strategy where all responses count even if after use of rescue therapy. Sensitivity analyses at Week 12 using a composite strategy may be explored for the responder endpoints if appropriate. Any substantial use of rescue therapy after Week 6, where substantial is as defined in Section 4.2.6.3, or use of restricted medication at any time post-baseline will impute the participant as a non-responder at Week 12.

The proportion of responders ( $\text{UAS7} \leq 6$ ) at Week 52 and the proportion of participants with complete UAS7 response ( $\text{UAS7} = 0$ ) at Week 52 will be analysed as described above, comparing effects on the Q4W and Q8W maintenance regimens.

#### **4.2.7.3 Hives severity score (HSS7)**

The change from baseline in HSS7 at Weeks 12 and 24 will be analysed using the same MMRM method as the key secondary endpoint (Section 4.2.7.1).

The change from baseline in HSS7 at Week 52 will be analysed with MMRM model as described above, comparing effects on the Q4W and Q8W maintenance regimens.

Descriptive summary statistics for scores and change from baseline will be produced by treatment group and visit.

#### **4.2.7.4 Itch Severity Score (ISS7)**

The change from baseline in ISS7 score at Week 24 will be analysed using the same MMRM method as the key secondary endpoint (Section 4.2.7.1).

The change from baseline in ISS7 at Week 52 will be analysed with MMRM model as described above, comparing effects on the Q4W and Q8W maintenance regimens.

Descriptive summary statistics for scores and change from baseline will be produced by treatment group and visit.

#### **4.2.7.5 Time to $\geq 5$ point decrease in ISS7**

The time to  $\geq 5$  point decrease (clinically relevant decrease) for ISS7 will be summarised by treatment group.

For time to first clinically relevant decrease, Kaplan Meier summary statistics will be presented by treatment group. The number of participants with at least one  $\geq 5$  point decrease, number of participants censored, and 25th percentile, median and 75th percentile with 95% CIs (calculated using the complementary log-log transformation) will be presented if calculable. Results will be displayed in Kaplan Meier plots.

#### **4.2.7.6 Measures of angioedema activity**

Measures of angioedema activity will be assessed in the overall population and repeated in participants with angioedema at baseline and in those with history angioedema.

Descriptive summaries of proportion of angioedema free days over the past 7 days, and proportion of patients with angioedema in the past 7 days, will be produced by treatment group and visit. A statistical model may also be used to analyse this data if appropriate (MMRM analyses, see Section [4.2.7.1](#)).

For the follow-up question, the frequency and percentages of each response over the past 7 days will be presented for number of participants and for number of responses per participant, presented by treatment group and visit.

The summaries will also be presented for durations of Week 4-12 and Week 4-24.

#### **4.2.7.7 Urticaria Control Test (UCT)**

Change from baseline in UCT at Weeks 12 and 24 will be analysed using the same MMRM method as the key secondary endpoint (see Section [4.2.7.1](#)).

The change from baseline in UCT at Week 52 will be analysed with MMRM model as described above, comparing effects on the Q4W and Q8W maintenance regimens.

The UCT score and changes from baseline will be summarised by treatment group and visit. The number and percentage of participants with UCT score of <12 (poorly controlled urticaria) and  $\geq 12$  (well controlled urticaria) will be presented by treatment group and visit.

#### **4.2.7.8 Chronic Urticaria Quality of Life Questionnaire (CU-Q2oL)**

Change from baseline in CU-Q2oL overall score at Weeks 12 and 24 will be analysed using the same MMRM method as the key secondary endpoint (see Section [4.2.7.1](#)).

Both the overall score and domain scores and changes from baseline will be summarised by treatment group and visit.

#### **4.2.7.9 Dermatology Life Quality Index (DLQI)**

Change from baseline in DLQI overall score at Weeks 12 and 24 will be analysed using the same MMRM method as the key secondary endpoint (see Section [4.2.7.1](#)).

Both the overall score, summed effects on life scores and domain scores, will be summarised by treatment group and visit.

#### **4.2.7.10 Serum benralizumab concentration**

Serum benralizumab concentration will be summarised using descriptive statistics at each visit by treatment group based on the safety analysis set.

#### **4.2.7.11 Anti-drug antibodies (ADA)**

Anti-drug antibodies to benralizumab will be summarised using descriptive statistics at each visit by treatment group based on the safety analysis set. The ADA titres-time profiles of benralizumab by treatment group will be generated. The impact of ADA on PK and eosinophil level will be assessed. The potential association of ADA with safety and efficacy will be evaluated.

Further details are provided in [Appendix 8.2](#).

#### **4.2.8 Safety Analyses**

Safety analyses will be performed using the safety analysis set. Summaries for the first 24 weeks will be presented by the 3 induction dose treatment groups as noted in Section [4.2](#). Summaries for the overall study period will be presented by the 5 randomised treatment sequences, including totals for the Q4W and Q8W dose regimens.

A small number of key tables will also be presented for data in the extension period alone to explore the safety profile in the second 6 months of study treatment were a direct comparison of Q4W versus Q8W dosing can be made for patients previously receiving benralizumab, and to summarise time on benralizumab alone for patients previously receiving placebo.

Participants will be analysed according to the treatment they received. In general, the baseline value for statistical analysis is the last non-missing value prior to administration of the first dose of IP. Safety data will be presented using descriptive statistics. No safety data will be imputed.

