4.1.2 Investigational Product Dosing Regimen

Participants who meet entry criteria will be randomised 3:3:3:3:4 by the interactive voice/web response system (Interactive Voice Response System [IVRS]/Interactive Web Response System [IWRs]) to one of the 5 treatment sequences described in Section [4.1](#).

[Figure 3](#) presents an overview of the IP that will be administered for each randomised treatment group.

Figure 3 Investigational Product Administration

^a In the extension period, participants will receive benralizumab on a Q8W or Q4W dosing regimen, as predetermined at randomisation (Visit 2). Participants randomised to receive benralizumab Q8W in the extension period will also receive placebo at intervening study visits when they are not receiving benralizumab.

Q4W, every 4 weeks; Q8W, every 8 weeks.

Dosing Regimen at Visits 2, 3, and 4 (Initial Double-blind 12-week Treatment Period)

All participants will receive randomised double-blind study medication Q4W at Visits 2, 3 and 4 (ie, Weeks 0, 4, and 8; [Figure 3](#)).

Dosing Regimen at Visits 5, 6, and 7

Participants randomised to receive either 60 mg or 30 mg benralizumab during the initial 12-week period will receive 30 mg benralizumab Q4W at Visits 5, 6 and 7 (ie, Weeks 12, 16 and 20; [Figure 3](#)).

Participants receiving placebo will continue to receive placebo ([Figure 3](#)).

Dosing Regimen at Visits 8 Through 14

At Week 24 (Visit 8), participants initially randomised to benralizumab 60 mg or benralizumab 30 mg will receive benralizumab 30 mg Q4W or Q8W according to their original randomisation at Week 2. Participants randomised to the Q8W regimen will receive placebo at Week 24 and benralizumab 30 mg at Week 28 ([Figure 3](#)).

At Weeks 24, 28, and 32 (ie, Visits 8, 9 and 10), participants initially randomised to placebo will receive benralizumab 30 mg Q4W. At Week 36 (ie, Visit 11), participants randomised initially to placebo will receive benralizumab 30 mg Q8W; these participants will receive placebo at Week 36 and benralizumab 30 mg at Week 40 (Visit 12) ([Figure 3](#)).

Participants transitioned to the benralizumab 30 mg Q8W dosing regimen will remain on the Q8W dosing regimen. Participants will continue to receive SC injections Q4W at the study site visits; thus, participants receiving benralizumab 30 mg Q8W will receive placebo at every other site visit ([Figure 3](#)).

The final dose of benralizumab or placebo will be administered at Week 48 (Visit 14).

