9.4.3 Safety Analyses

Safety analyses will be performed using the safety analysis set.

Analyses will be presented for the overall study period split by the 5 treatment sequences and presented separately for the first 24 weeks split by the 3 induction dose treatment groups as noted in Section 9.2.

Participants will be analysed according to the treatment they received.

In general, the baseline value for statistical analysis is the last non-missing value prior to administration of the first dose of IP. Details will be described in the SAP.

Adverse Events

Adverse events will be coded using the most recent version of the Medical Dictionary for Regulatory Activities that will have been released for execution at AstraZeneca/designee.

Safety data will be presented using descriptive statistics unless otherwise specified in the SAP.

Adverse events will be presented for each treatment group by system organ class and preferred term, including the number and percentage of participants reporting at least one event, number of events and exposure-adjusted rates, where appropriate.

An overview of AEs will be presented for each treatment group, including the number and percentage of participants with any AE, AEs with outcome of death, serious AEs, and AEs leading to discontinuation of IP.

Separate AE tables will be provided taking into consideration the relationship as to IP assessed by the Investigator, maximum intensity, seriousness, death and events leading to discontinuation of IP, as well as other action taken related to IP.

Key participant information will be presented for participants with AEs with outcome of death, serious AEs, and AEs leading to discontinuation of IP.

An AE listing for the safety analysis set will cover details for each individual AE.

Full details of AE analyses will be provided in the SAP.

Treatment Emergent

The following events are considered treatment emergent:

- Adverse events with an onset date on or after the first dose of IP
- Worsening of pre-existing events on or after first dose of IP

Clinical Laboratory Safety Assessments

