##### **4.2.8.1 Adverse Events**

TEAEs will be summarised separately for the on-treatment, on-study, and post-treatment periods, as defined in Section [3.4.1](#). The primary period of interest for safety summaries will be the on-treatment period and this is the only period that will be used for the placebo controlled first 24 weeks summaries. Limited summaries will be produced for the on-study and post-treatment periods for the whole study summaries only. AEs in the pre-treatment period (with start date prior to the first dose of IP) will be listed for the placebo-controlled treatment period at primary database lock only.

All summaries will be presented by treatment group and key tables will include exposure-adjusted rates to account for any differences in follow up.

The rate of TEAEs per person-years at risk will be calculated as (number of participants reporting the TEAE) / (total IP exposure with participants at risk of TEAE) for on-treatment and on-study periods. The post-treatment AEs will be listed. The total period at risk for each participant will be the duration of the on-treatment, post-treatment and on-study periods as defined in Section [3.4.1](#). Rates will be expressed in terms of events per 100 participant-years.

An overall summary table will be produced showing the number, percentage, and exposure-adjusted rate of participants with at least 1 TEAE in any of the following categories; TEAEs, SAEs, AEs with outcome of death, and AEs leading to discontinuation of IP (DAEs). AEs will be presented for each treatment group by system organ class and preferred term, including the number and percentage of participants reporting at least one event, number of events and exposure-adjusted rates, where appropriate.

TEAEs, AEs with outcome of death, SAEs and DAEs will be summarised by system organ class (SOC) and preferred term (PT) assigned to the event by MedDRA. For each PT, the number, percentage and exposure-adjusted rate of participants reporting at least one occurrence will be presented (ie, multiple occurrences of an AE for a participant will only be counted once).

A summary of the most common (frequency of >5%) TEAEs will be presented by PT. AEs and SAEs causing discontinuation of the study treatment and SAEs causing discontinuation from the study will also be summarised.

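### No adverse-event summary is planned for Weeks 0–12, the only period in which the 60 mg and 30 mg groups are assigned different doses, so the planned tables dilute rate and ratio contrasts between them

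*SAP*

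**What the plan says.** **Dosing.** Protocol 4.1.2 sets the induction period: "All participants will receive randomised double-blind study medication Q4W at Visits 2, 3 and 4 (ie, Weeks 0, 4, and 8". At the next three visits, participants assigned either benralizumab dose "will receive 30 mg benralizumab Q4W at Visits 5, 6 and 7 (ie, Weeks 12, 16 and 20". SAP 1.1.2 repeats this.

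**Safety tables.** SAP 4.2.8 plans two main layouts: "Summaries for the first 24 weeks will be presented by the 3 induction dose treatment groups", and "Summaries for the overall study period will be presented by the 5 randomised treatment sequences". It adds a small set of key tables for the extension alone. Protocol 9.4.3 has the same structure: "Analyses will be presented for the overall study period split by the 5 treatment sequences and presented separately for the first 24 weeks".

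**Adverse-event window.** SAP 3.4.1 runs the double-blind on-treatment window from the first dose to the day before the first extension dose. For those who do not enter the extension it ends 30 days after the last double-blind dose. It is not divided at Week 12. SAP 4.2.8.1 says of the on-treatment period that "this is the only period that will be used for the placebo controlled first 24 weeks summaries". Events are reported both as the percentage of participants affected and as exposure-adjusted rates. All safety output is descriptive.

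**Other outputs.** Vital signs are summarised by visit (SAP 4.2.8.3). Injection-site reactions are also summarised by number of administrations, and every adverse event is listed (SAP 4.2.8.1).

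**The concern.** Protocol 4.3 makes evaluation of the induction dose a goal of the trial. The primary efficacy contrast is read at Week 12, after three doses at the assigned level. Adverse events are read over twice that time, and in the second half the two benralizumab groups are on the same dose. Benefit and harm of the 60 mg induction are therefore not described over the same period.

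If 60 mg carries an excess of adverse events while it is being given, the planned rates and ratios against 30 mg will show a smaller contrast than the one that existed during induction. Injection-site reactions have a further complication. Every participant receives two injections per visit at Weeks 0, 4 and 8 and one per visit afterwards (Protocol 6.3.2), so a 24-week table mixes two injection schedules.

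**Working it through.** **The plan's own figures.** The documents state no adverse-event rate, precision or power for safety. The only power figure is 90% for ISS7 at Week 12. With 36 v 54 participants after 10% dropout, 4.7/(6 × √(1/36 + 1/54)) = 3.64; less the two-sided 2.5% critical value of 2.24 this leaves 1.40, or about 92% power (91% by noncentral t). The figure reproduces but does not bear on this point.

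**1. Share of time at 60 mg (from the dosing sections)**
- First 24 weeks: 3 of 6 doses, and 12/24 weeks = 50%.
- Planned cumulative dose to Week 24: 3×60 + 3×30 = 270 mg v 6×30 = 180 mg, ratio 1.5. Over Weeks 0–12 it is 180 v 90 mg, ratio 2.0.
- Whole-study tables: 12/52 weeks = 23%.

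**2. Mean event rate, all events counted.** Assume a constant hazard, a hazard ratio k for 60 mg v 30 mg in Weeks 0–12, a ratio of 1 afterwards, and no carry-over.
- Rate ratio over 24 weeks = (12k + 12)/24. For k = 2 this is 1.5; for k = 3 it is 2.0.
- Share of the excess rate kept = 12/24 = 50%.
- If the excess lasts c weeks past Week 12 (assumed), the share kept is (12 + c)/24: 67%, 83% and 100% for c = 4, 8 and 12.

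**3. Percentage of participants with an event.** Let p be the 12-week risk on 30 mg (assumed 5–30%) and q = 1 − p.
- Weeks 0–12: risks 1 − q^k v 1 − q, difference q − q^k.
- Weeks 0–24: risks 1 − q^(k+1) v 1 − q², difference q² − q^(k+1) = q(q − q^k).
- Share of the difference kept = q, whatever k is.

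For k = 2:

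| p | Risk difference 0–12, points | Risk difference 0–24, points | Kept | Risk ratio 0–12 | Risk ratio 0–24 | First-event rate difference kept |
|---|---|---|---|---|---|---|
| 5% | 4.8 | 4.5 | 95% | 1.95 | 1.46 | 52% |
| 10% | 9.0 | 8.1 | 90% | 1.90 | 1.43 | 54% |
| 20% | 16.0 | 12.8 | 80% | 1.80 | 1.36 | 58% |
| 30% | 21.0 | 14.7 | 70% | 1.70 | 1.29 | 63% |

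The last column takes time at risk as ending at the first event. Example, p = 10%: with 30 mg hazard h, time at risk on 60 mg is [(1 − 0.81)/2 + 0.81 × 0.10]/h = 0.176/h, and 0.271/0.176 = 1.54, so 54% of the excess remains. Across k = 1.5, 2 and 3 the share is 52–68%.

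**4. Scale.** With 60 per group, two-sided 5%, p = 10% and k = 2, a test of 60 mg v 30 mg would have about 29% power over 12 weeks and 18% over 24. No such test is planned. The figures only show that information is thin in either window.

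**The case against.** The strongest defence is that participants are randomised to sequences, and 60 mg followed by 30 mg is one of the regimens under study. The three groups are pooled by initial dose to Week 24 throughout. Protocol 4.3 says that Weeks 12–24 serve to look for differential effects after the induction doses. A 24-week table is thus a correct summary of the regimen as randomised, and it catches delayed events that a 12-week table would miss.

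Carry-over is also plausible. Contraception and live-vaccine rules run for 12 weeks after the last dose (Protocol 5.1 and 6.5.4), and Protocol 4.3 reports near-complete eosinophil depletion with 8-weekly dosing in asthma. Neither is a washout figure, but both caution against treating Week 12 as a clean break. Finally, safety is descriptive, and Protocol 4.3 frames the induction-dose goal in terms of onset and effectiveness.

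All of this stands, and it rules out several stronger readings that a reader might infer:

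- *The 24-week tables are the only safety output that separates the doses.* They are not. The five-sequence tables also do so, with more dilution, and vital signs are shown at the induction visits.
- *Any excess risk is halved.* Halving applies to a mean event rate under constant hazard without carry-over. Events from Weeks 0–12 remain counted at Week 24, so the difference in percentages is mostly kept.
- *The 24-week window is an error, or Weeks 0–12 should become the main period.* The documents support neither; a shorter main period would push delayed events into secondary tables.

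The defence does not supply adverse events, serious events or hypersensitivity by dose group for Weeks 0–12. Listings hold the dates but do not summarise by group.

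**Conclusion.** The gap is real but narrow. No adverse-event summary isolates the 12 weeks in which the assigned benralizumab doses differ. The 24-week tables pool equal time at 60 mg and 30 mg in the 60 mg group, and the whole-study tables have 23% of the time at 60 mg.

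Over 24 weeks a mean excess event rate is diluted by up to half, and by less if the effect of the 60 mg doses lasts past Week 12. Risk ratios shrink too, for example from 1.90 to 1.43 at a 12-week risk of 10% and a hazard ratio of 2. The absolute difference in the percentage of participants affected keeps about 70–95%. These sizes rest on assumed risks of 5–30%, constant hazards and an excess confined to Weeks 0–12. The documents give no adverse-event rates, timing or washout figure, so the actual dilution cannot be fixed from them. Nor do they show that 60 mg will look falsely safe. This is a cheap improvement to the plan and does not correct an invalid analysis.

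**What to change.** Before the primary database lock, keep the 24-week tables in SAP 4.2.8 as the placebo-controlled summary and add beside them a descriptive adverse-event summary for Weeks 0–12 by the three induction groups.

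- **Window** (to be defined in SAP 3.4.1): first dose to the day before the Week 12 dose, or last dose + 30 days if treatment stopped earlier and that date comes first.
- **Content:** overview of treatment-emergent events, system organ class and preferred term, injection-site reactions, and hypersensitivity, with percentages and exposure-adjusted rates as in the 24-week tables.

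**Cost:** a few more tables from data already collected; no alpha is used and nothing planned is removed. The shorter window holds fewer events, and delayed events appear only in the 24-week tables, so the two sets should be read together.
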